### 1.1 Primary Endpoint

To observe the efficacy and safety of Lexette and Sorilux in moderate plaque type psoriasis for 2 weeks and then maintenance of success compared to vehicle with Sorilux for the next 6 weeks. Primary endpoint is the percent of subjects who maintain clear or almost clear on PGA at week 8.

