## 2 STUDY DESIGN

This is a single-center, double-blind study. Approximately 30 qualified subjects will be enrolled into a 8 weeks study. Subjects will be randomized to study treatment at a 1:1 ratio: of Lexette plus Sorilux for 2 weeks versus Lexette plus vehicle for 2 weeks. Those subjects who are clear or almost clear at the end of 2 weeks will be re-randomized into Sorilux for 6 weeks versus vehicle for 6 weeks at 1:1 ratio. All adverse events and con meds will be recorded throughout the study.

Group A n = 15	Lexette + Sorilux for 2 weeks
Group B n = 15	Lexette + plus Vehicle Foam for 2 weeks

Subjects will attend a Screening Visit/Baseline visit and if found eligible will be randomized to study treatment. Patients will be counselled on the use of the study medication and the medications will be labelled for the appropriate group as noted above.

Total study period is 8 weeks. Study visits will be, screening/baseline, week 2 and week 8. Study assessments will be at each visit: BSA, PGA, Itch VAS, DLQI, and TLSS in addition to standard medical assessments. There will be a standard prohibited medication/treatment and washout periods.

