## 4 TREATMENT OF SUBJECTS AND FOLLOW-UP

### 4.1 Study Procedures

#### 4.1.1 Assessment Schedule

Procedures/Non-Procedure Description	Screening and Baseline	Weeks 2	Week 8
Informed Consent	X		
Medical History and Demographics	X		
Inclusion/Exclusion Criteria	X		
Initial Prior/Concurrent Medications	X		
Concurrent Medications subsequent visit		X	X
Vital Signs (includes height/weight)	X	X	X
Re-Randomization		X	
Abbreviated Physical Exam		X	X
VAS	X	X	X
DLQI	X	X	X
Complete Physical Examination	X		
TLSS scoring	X	X	X
Pregnancy Test	X	X	X
Adverse event assessment and reporting if applicable	X	X	X
Clinical severity/efficacy assessments by investigator (BSA, PGA)	X	X	X
Pharmacy Dispense and collection /Drug Accountability	X	X	X

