## **6 ASSESSMENTS OF SAFETY**

### **6.1 Safety Assessments**

Throughout the study, subjects will be monitored for signs and symptoms of adverse events. All adverse events and con meds will be recorded throughout study. An *adverse event* is any pathological or unintended change in the structure, function or chemistry of the body that occurs during the study, irrespective of causality, including any illness, injury, toxicity, sensitivity, or sudden death. The condition must either not be present pre-study or must worsen in either intensity or frequency during the study. A *serious adverse event* is any untoward medical occurrence, that, at any dose:

- results in death;
- is life-threatening;
- requires in-patient hospitalization or prolongation of existing hospitalization;
- results in persistent or significant disability/incapacity;
- is a congenital anomaly/birth defect; or
- is an important medical event.

An *unexpected adverse event* is any treatment-related adverse event, which is not identified in nature, severity, or frequency in current literature on the test product.

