### **7.2 Analyses**

Statistical analyses will be conducted on an intent-to-treat population that includes all subjects who were enrolled and received study medication. Due to small sample size and exploratory nature of the study, descriptive statistics will be performed using SAS. Any additional statistical analyses will be performed as appropriate and detailed in the final report. All statistical tests will be two-sided and interpreted at a 5% significance level. Descriptive statistics (i.e., mean, standard deviation, etc.) will be provided for all continuous variables and frequencies for all categorical variables collected in this study. Summary tables will be used to present patient population characteristics at Baseline; data from the study questionnaires will be included. Analyses of study treatment will be performed using an ANCOVA technique with the Baseline value as the covariate provided the necessary assumptions for parametric tests are satisfied. The Wilcoxon Rank-Sum test will be used if the necessary assumptions for parametric tests are not satisfied. Mean scores will also be analyzed. Safety analyses will be performed in terms of incidence and severity of local tolerance signs and symptoms and adverse and/or unexpected events.

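### Section 7.2 plans a local tolerance analysis, but no visit schedules a local tolerance assessment and no signs or scale are defined, so the data would come only from general adverse event recording

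*Combined protocol and SAP*

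**What the plan says.** Safety is part of the stated aim. Section 1.1 opens with "To observe the efficacy and safety of Lexette and Sorilux in moderate plaque type psoriasis for 2 weeks", although the primary endpoint it then defines is PGA success at week 8, an efficacy measure.

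The safety analysis is one sentence in section 7.2: "Safety analyses will be performed in terms of incidence and severity of local tolerance signs and symptoms and adverse and/or unexpected events".

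On data collection, section 2 states: "Study assessments will be at each visit: BSA, PGA, Itch VAS, DLQI, and TLSS in addition to standard medical assessments". The schedule in section 4.1.1 has a row "Adverse event assessment and reporting if applicable", marked at screening/baseline, week 2 and week 8. It also has a complete physical examination at baseline and an "Abbreviated Physical Exam" at weeks 2 and 8, whose content is not described. Section 6.1 adds: "Throughout the study, subjects will be monitored for signs and symptoms of adverse events". Section 6.2.2 requires every adverse event to go into the CRF with its severity and its start and end dates.

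**The concern.** The analysis section treats local tolerance and adverse events as two things, while the collection sections provide for only one of them. The regimen puts two topical products on the same skin, twice daily and five minutes apart (section 4.2.1, dispensation and dosage), so skin reaction at the application site is a natural safety question, and section 7.2 names it first.

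What is at stake is the meaning of a low count. If each sign is graded at each visit, a zero means that someone looked and found nothing. If local reactions appear only when they are judged to be adverse events and written up as such, an empty record may mean no reaction, or a reaction taken for psoriasis, or a symptom nobody asked about. A report that no local reactions were seen could then be read as evidence of good tolerance. This cannot be repaired later, because a grade not taken at the visit cannot be reconstructed.

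**Working it through.** The plan gives no figure tied to this analysis, and section 7.1 declines a formal sample size justification, so there is nothing to recompute. The check sets what section 7.2 needs against what the other sections collect.

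**What section 7.2 needs.** Which signs and symptoms count, when they are looked for, and how severity is graded.

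**Where that could be found:**

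- *Section 2, list of assessments:* BSA, PGA, itch VAS, DLQI, TLSS and unspecified standard medical assessments. Local tolerance is not named.
- *Section 4.1.1, schedule:* 0 of 16 rows names local tolerance.
- *Visit lists (section 4.1.2, section 4.1.3 and the week 8 list that follows):* 0 of 3.
- *Sections 5 and 6:* section 5 covers BSA, PGA and TLSS; section 6 covers adverse events. Neither defines a tolerance item or scale.
- *Readable forms:* PGA, BSA, itch scale and DLQI. None is a tolerance form.

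In the readable text, the term occurs only in section 7.2.

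**What adverse event recording supplies.**

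- Assessment is marked at 3 of 3 visits, and monitoring runs throughout the study.
- The definition in section 6.1 is broad: "irrespective of causality, including any illness, injury, toxicity, sensitivity, or sudden death". An application-site reaction fits under toxicity or sensitivity.
- Severity and dates are recorded, so events can be counted, graded and assigned to the 2-week or the 6-week phase.
- There is no list of signs to ask about or inspect, and no severity scale is defined.

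**Whether another measure fills the gap.**

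- PGA grades plaque elevation, scaling and erythema as signs of psoriasis. A PGA of 1 (almost clear) allows erythema up to moderate, so redness from irritation could sit inside a success score without being identified as such.
- TLSS is an efficacy score for the target lesion (section 5.3).
- Itch VAS and DLQI are secondary endpoints. The first DLQI question pools itch, soreness, pain and stinging and asks how the skin has been, not how it reacted to the foam.

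None of these is set up to distinguish disease from an application-site reaction.

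**Result.** Adverse event assessment is planned at 3 of 3 visits; a dedicated local tolerance assessment is planned at 0 of 3. The local tolerance component rests on general adverse event recording alone.

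**The case against.** The strongest reply is that the plan does collect local reactions. Adverse event assessment appears at every visit, the definition includes toxicity and sensitivity, and every event carries a severity. Incidence and severity are the two quantities section 7.2 names, and both can be derived from those records. The investigator also examines and grades the skin at every visit. On this view the mismatch is one of wording, and editing one phrase in section 7.2 closes it.

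Much of this stands, and it rules out several stronger readings that a reader might infer:

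- *That the analysis has no data source or cannot be run.* Application-site reactions recorded as adverse events give a partial source.
- *That safety reporting is ad hoc.* It is scheduled at all three visits. In the schedule row, the words about applicability can be read as qualifying the reporting rather than the assessment, and the visit lists carry no qualifier.
- *That the adverse event definition defeats the analysis.* Section 6.1 says "The condition must either not be present pre-study or must worsen in either intensity or frequency during the study". Counting only new or worsened conditions is ordinary incidence, and section 7.2 does not promise a rate at each visit.
- *That half of the efficacy-and-safety aim is unsupported.* The adverse event component has a clear source.
- *That the small arms show the size of this defect.* With no events among 15 subjects, the exact two-sided 95% upper limit is 1 - 0.025^(1/15) = 21.8%. That reflects sample size and would be the same after the fix. No maintenance arm size is stated; by the same formula the limit runs from 70.8% at an assumed 3 per arm to 21.8% at the maximum of 15.

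The reply does not answer the separate naming of local tolerance in section 7.2, or the absence of a sign list, scale and sign-by-sign elicitation. Editing the wording would make the plan consistent, but it would also give up the tolerance information that the plan says it wants.

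**Conclusion.** The concern holds as a gap between a named analysis and its data collection: section 7.2 promises local tolerance results separate from adverse events, no visit schedules that assessment, and no signs, scale or baseline grade are defined. Its size is a count, 0 of 3 visits and 0 of 16 schedule rows, against 3 of 3 visits for adverse events. The documents give no basis for estimating how many local reactions would be missed.

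It should be corrected before enrolment because the missing grades cannot be recovered afterwards. It does not affect the primary endpoint or the adverse event component of the safety analysis.

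The conclusion assumes that no tolerance form exists outside the readable text. The CRF is not among the documents, the TLSS table is not visible and the DLQI form breaks off, so a form cannot be wholly excluded. The schedule and visit lists are legible, however, and that is where such an assessment would be listed.

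**What to change.** Add one row to section 4.1.1, and the matching line to the three visit lists, for local tolerance at the application site. Fix the signs and symptoms and a 0-3 scale with worded grades before enrolment, so that the list is not left to choice at the visit. Have the blinded investigator grade them at baseline, week 2 and week 8. In section 7.2, state that results will be summarised by arm and phase: week 2 by initial treatment, week 8 by maintenance treatment. Present them beside the baseline grade, because some signs on plaques before treatment will be psoriasis itself.

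The cost is a small added grading burden at visits that already include skin grading, a CRF item, and a protocol change made in consultation with the IRB under section 8.2. No visit is added and treatment is unchanged.

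If the sponsor declines, restrict section 7.2 to application-site adverse events by severity and make no separate local tolerance claim in the report. That costs one phrase and aligns the analysis with the data, but a low count would still have to be read as events reported, not as tolerance assessed.

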## **8 RESPONSIBILITIES OF THE INVESTIGATOR**

### **8.1 Good Clinical Practice**

Investigators must adhere to the procedures outlined in this Study Protocol. The procedures set out in this study protocol, pertaining to the conduct, evaluation, and documentation of this study, are designed to ensure that the Investigator abides by GCP as described in the ICH Guidelines Topic E6: "Guideline for Good Clinical Practice." Compliance with these regulations also constitutes compliance with the ethical principles described in the current revision of the Declaration of Helsinki. The study will also be carried out in keeping with local legal and regulatory requirements.

### **8.2 Ethics**

The appropriate IRB must review the Study Protocol and Informed Consent Form prior to initiating the study. Any significant modifications to the IRB-approved protocol or informed consent must be made in consultation with the IRB.

### **8.3 Confidentiality of Subjects**

Any information that identifies subjects with respect to this research study will be kept confidential. However, records identifying the subject may be inspected by representatives of the IRB and/or the FDA. Subjects' identity will remain strictly confidential during all record reviews, as well as in any publication that may result from this research. Subjects will be identified by study code only; their names will not be used.

### **8.4 Informed Consent**

Informed consent is a process that is initiated prior to the individual's agreeing to participate in the study and continuing throughout the individual's study participation. Appropriate discussion of risks

and possible benefits of this therapy will be provided to the subjects. Consent forms describing in detail the study interventions/products, study procedures and risks will be given to the subject and written documentation of informed consent is required prior to starting intervention/administration study product.

Consent forms will be IRB approved and the subject will be asked to read and review the document. Upon reviewing the document, the investigator will explain the research study to the subject and answer any questions that may arise. The subjects will sign the informed consent document prior to any procedures being done specifically for the study. The subjects should have the opportunity to discuss the study with their surrogates or think about it prior to agreeing to participate. The subjects may withdraw consent at any time throughout the course of the trial. A copy of the informed consent document will be given to the subjects for their records. The rights and welfare of the subjects will be protected by emphasizing to them that the quality of their medical care will not be adversely affected if they decline to participate in this study.

### **8.5 Data Handling and Record Keeping**

Investigators must ensure that proper source documentation for all study activities are diligently maintained and securely kept. Investigators will transfer all relevant data from source documents to the Case Report Form as stipulated in this Study Protocol and his/her signature on the Case Report Form guarantees completeness and integrity of these data. Investigators will maintain reliable study device dispensing/dosing records and will store study supplies in a secure, locked location. In addition, Investigators will ensure that all study-related source documentation and Case Report Forms will be maintained for a period of two years after the conclusion of the study.

### **8.6 Direct Access to Source Data/Documents**

Investigators must ensure that the Informed Consent Form clearly permit study-related monitoring, audits, IRB review, and regulatory inspections providing direct access to source data and documents.

## Physicians Global Assessment Psoriasis

\_\_\_ 0. Clear: no signs of psoriasis (Hyper/hypopigmentation changes alone are acceptable).  
Plaque elevation = 0. Scaling = 0. Erythema = +/- (hyperpigmentation, pigmented macules,  
diffuse faint pink or red coloration).

\_\_\_ 1. Almost Clear: Plaque elevation = +/- (possible but difficult to ascertain whether there  
is slight elevation above normal skin). Scaling = +/- (surface dryness with some white  
discoloration). Erythema = up to moderate (up to definite red coloration).

\_\_\_ 2. Mild: Plaque elevation = slight (slight but definite elevation, typically edges are  
indistinct or sloped). Scaling = fine (fine scale partially or mostly covering lesions). Erythema  
= up to moderate (up to definite red coloration).

\_\_\_ 3. Moderate: Plaque elevation = moderate (moderate elevation with rough or sloped  
edges). Scaling = coarse (coarse scale covering most or all of the lesions). Erythema =  
moderate (definite red coloration).

\_\_\_ 4. Severe: Plaque elevation = marked (marked elevation typically with hard or sharp  
edges). Scaling = coarse (coarse, nontenacious scale predominates, covering most of all  
lesions). Erythema = severe (very bright red coloration).

[figure not shown]
### PSORIATIC BODY SURFACE AREA

BODY AREA	% of BODY AREA AFFECTED	% of TOTAL BODY SURFACE AREA	% of TOTAL BODY SURFACE AFFECTED
HEAD		10%	
TRUNK		30%	
UPPER LIMBS		20%	
LOWER LIMBS		40%	
TOTAL	-----	100%	

(Multiply the numerical percent of the body part affected x the % of the total body surface area for each body area. Then add the % of total body surface affected for each area to determine the total BSA. For example: If the % of the head affected is 10, multiply ten by the % of total body surface area (10% = 0.1) for a total of 1% of Total Body Surface Area.)

## ITCH RATING SCALE

Draw a single, vertical line on the scale below to indicate how bad you feel your itching is today:

### Dermatology Life Quality Index (DLQI)

Score:

**The aim of this questionnaire is to measure how much your skin problem has affected your life OVER THE LAST WEEK. Please tick  one box for each question.**

- |    |  |                                    |                                   |                                     |                                     |                                       |
|----|--|------------------------------------|-----------------------------------|-------------------------------------|-------------------------------------|---------------------------------------|
| 1. | Over the last week, how itchy, sore, painful or stinging has your skin been?   | Very much  | A lot     | A little    | Not at all  |                                       |
| 2. | Over the last week, how embarrassed or self conscious have you been because of your skin?  | Very much  | A lot     | A little    | Not at all  |                                       |
| 3. | Over the last week, how much has your skin interfered with you going shopping or looking after your home or garden ?      | Very much  | A lot     | A little    | Not at all  | Not relevant  |
| 4. | Over the last week, how much has your skin influenced the clothes you wear?   | Very much  | A lot     | A little    | Not at all  | Not relevant  |
| 5. | Over the last week, how much has your skin affected any social or leisure activities?  | Very much  | A lot     | A little    | Not at all  | Not relevant  |
| 6. | Over the last week, how much has your skin made it difficult for you to do any sport ?  | Very much  | A lot     | A little    | Not at all  | Not relevant  |
| 7. | Over the last week, has your skin prevented you from working or studying ?   | Yes        | No        |                                     |                                     | Not relevant  |
|    | If "No", over the last week how much has your skin been a problem at work or studying ?  | A lot      | A little  | Not at all  |                                     |                                       |
| 8. | Over the last week, how much has your skin created problems with your partner or any of your close friends or relatives ? | Very much  | A lot     | A little    | Not at all  | Not relevant  |
| 9. | Over the last week, how much has your  | Very much  |                                   |                                     |                                     |                                       |

at the base of the can's rim by gently pushing back (away from the piece) on the nozzle.

2. Shake the SORILUX Foam can before use.

3. Turn the SORILUX Foam can upside down and press the nozzle.

4. Dispense a small amount of SORILUX Foam into the palm of your hand.

5. Use enough SORILUX Foam to cover the affected area with a thin layer.

Apply SORILUX Foam to your scalp when your hair is dry. Part your hair and apply directly on the affected area. Gently rub the foam into the affected area until it disappears into the skin.

6. Avoid getting SORILUX Foam on your face or in or near the eyes, mouth, or vagina. If SORILUX Foam gets on your face or in or near your eyes, rinse with water. Wash hands after applying SORILUX Foam unless your hands are a treated area.

#### **Instructions for applying Lexette foam:**

**Step 1: Before applying Halobetasol Propionate Topical Foam for the first time, remove cap and break the small tab at the base of the actuator by gently pushing the actuator away from the tab as shown. Do not break the hinge on the actuator.**

**Step 2: Shake the can well before use.**

**Step 3: Turn the can completely upside down.**

**Step 4: Press down on the actuator to dispense a small amount of the foam into the palm of your hand.**

**Step 5: Apply a thin layer of Halobetasol Propionate Topical Foam to the affected skin area. Gently rub Halobetasol Propionate Topical Foam into the affected skin until the foam disappears.**

**Repeat Steps 4 and 5 to all the affected areas as prescribed by your healthcare provider.**

**Step 6: After applying Halobetasol Propionate Topical Foam, put the cap back on the can.**

**Step 7: Wash your hands after applying Halobetasol Propionate Topical Foam unless you are using the medicine to treat your hands.**
